10.1 Compliance statement

This study will be conducted in accordance with this protocol and applicable national and local requirements for good pharmacovigilance practices.

10.2 Patient privacy

- All study information and documentation collected by the Investigator will be kept confidential. The Investigator must ensure that patient confidentiality is maintained. In eCRFs or other documents submitted to the Sponsor, the patient should not be identified by their names, but by a PIC (see section 9.2.6).
- The Investigator will keep a separate log of patient codes, names and addresses. This log and other documents not for submission to the Sponsor (e.g. ICF) should be maintained by the Investigator in strict confidentiality in the ISF.
- The medical information may be given to the patient's personal physician or to other appropriate medical personnel responsible for the patient's welfare, if the patient/patient's legal representative agrees.
- Site staff will be provided with a unique eCRF login information (username and password), giving access limited only to data of the site.

10.3 Approval of study protocol

- A notification of the planned study to the Competent Authority (CA) will be performed and a favourable opinion from the relevant EC will be obtained prior to the start of the study.
- The CA and EC will be notified about the end of the study and a report summarizing the study results will be sent to the CA and EC according to local legislation.
- If the study is terminated early or study enrolment must be suspended, the CA and EC will be notified according to local legislation.
- If mandated by local legislation enrolment can only be resumed after authorization by the CA and EC.

10.4 Protocol amendments

- Amendments to the study protocol may be made following the procedures specified by local laws and regulations.
- Substantial amendments to the study protocol (i.e. due to changes to the protocol or from new information relating to the scientific documents in support of the study) may be implemented only if the notification to the CA was performed and a favourable opinion of the EC have been obtained.

10.5 Informed consent

- Written informed consent will be obtained from each patient or (if the patient is unable to provide informed consent) the patient's legally authorized representative prior to the patient's study participation.
- In obtaining and documenting informed consent, the Investigator will comply with applicable legal requirements and with the ethical principles that have their origin in the Declaration of Helsinki; the consent process includes providing the patient with an appropriate explanation of the aims, methods, anticipated benefits, potential hazards and any other aspect of the study which may influence the patient's decision to participate. The Investigator will explain that the patients are completely free to refuse participation in the study and may withdraw at any time, without any consequences for their further care and without the need to justify their decision.

11. Management and reporting of adverse events/adverse reactions

11.1 Definitions

11.1.1 Adverse Events / Adverse Drug Reactions

- An adverse event (AE) is any untoward medical occurrence in a patient or study subject administered a MP and which does not necessarily have a causal relationship with this treatment.
 - An AE can therefore be any unfavourable and unintended sign (including an abnormal laboratory finding), symptom, or disease temporally associated with the use of a MP, whether or not considered related to the MP.
- An adverse drug reaction (ADR) is a response to a medicinal product which is noxious and unintended.
 - The definition of an adverse reaction implies at least a reasonable possibility of a causal relationship between a suspected medicinal product and an adverse event. An adverse reaction, in contrast to an adverse event, is characterised by the fact that a causal relationship between a MP and an occurrence is suspected.
 - For regulatory reporting purposes, if an event is spontaneously reported, even if the relationship is unknown or unstated, it meets the definition of an adverse reaction. Therefore, all spontaneous reports notified by healthcare professionals or consumers are considered suspected adverse reactions, since they convey the suspicions of the primary sources, unless the reporters specifically state that they believe the events to be unrelated or that a causal relationship can be excluded.
- A **treatment-emergent** AE/ADR is any AE/ADR that occurred only since time of the first MP (ropeginterferon alfa-2b) administration.

11.1.2 Solicited / Unsolicited Reports

- Solicited reports of suspected adverse reactions are those derived from organised data collection systems, which include clinical trials, non-interventional studies, registries, post-approval named patient use programmes, other patient support and disease management programmes, surveys of patients or healthcare professionals, compassionate use or name patient use, or information gathering on efficacy or patient compliance. Reports of suspected adverse reactions obtained from any of these data collection systems should not be considered spontaneous.
- A spontaneous report is an unsolicited communication by a healthcare professional,

or consumer to a competent authority, marketing authorisation holder or other organisation (e.g. regional pharmacovigilance centre, poison control centre) that describes one or more suspected adverse reactions in a patient who was given one or more medicinal products.

11.1.3 Causality

- Medical judgement should be used to determine the causal relationship between AEs and administered MP (ropeginterferon alfa-2b), considering relevant factors, such as pattern of reaction, temporal relationship, concomitant medication, concomitant diseases and relevant history. The following categories are used:
 - **Related** to MP (reasonable possibility): The temporal relationship of the clinical event to MP administration makes a causal relationship possible; and other drugs, therapeutic interventions or underlying conditions do not provide a sufficient explanation for the observed event. Reports including good reasons and sufficient information to assume a causal relationship in the sense that it is plausible, conceivable, or likely or reports containing sufficient information to indicate the possibility of a causal relationship in the sense of it not being impossible and not unlikely, although the connection may be uncertain or doubtful (e.g. due to missing data, insufficient evidence etc.).
 - Not related to MP (no reasonable possibility): The temporal relationship of the clinical event to MP administration makes a causal relationship unlikely; or other drugs, therapeutic interventions or underlying conditions provide a sufficient explanation for the event.
- Note that if causality is unknown, it should be attributed to the MP (ropeginterferon alfa-2b) until documented otherwise by the Investigator.

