2. Secondary objectives

- To describe the baseline characteristics of PV patients newly treated with ropeginterferon alfa-2b in routine post-authorization use.
- To evaluate the effectiveness of the risk minimization measures for the important, identified risk "hepatotoxicity".

- To further characterize the important, identified risk "hepatotoxicity" in subgroups of the patient population (i.e. with/without co-medication with nonsteroidal anti-inflammatory drugs, with/without pre-existing liver disease or baseline liver parameter elevation).
- To assess the incidence rate of thromboembolic adverse events and major adverse cardiac events (MACE) in PV patients newly treated with ropeginterferon alfa-2b in routine post-authorization use.
- To further evaluate cardiovascular safety in subgroups of the patient population (i.e. with/without cardiovascular risk factors, with/without pre-existing cardiovascular disease).

9. Research methods

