9.7.2 Methods of analysis

9.7.2.1 Primary safety endpoint

Incidence of (1) significant elevations of liver enzymes ALT, and/or AST, and/or GGT (≥3 times ULN) and/or bilirubin (>2 times ULN), and (2) treatment-emergent hepatobiliary adverse drug reactions in Part A (i.e. first 6 months of treatment).

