9.7.2.5 Additional subgroup analyses

- Subgroup analysis of incidence of significant elevations of liver enzymes and bilirubin for patients with and without co-medication with nonsteroidal anti-inflammatory drugs
- Subgroup analysis of incidence of significant elevations of liver enzymes and bilirubin for patients with and without pre-existing liver disease/or patients with baseline liver parameter elevation
- Subgroup analysis of incidence of treatment-emergent hepatobiliary adverse drug reactions for patients with and without co-medication with nonsteroidal anti-

inflammatory drugs

- Subgroup analysis of incidence of treatment-emergent hepatobiliary adverse drug reactions for patients with and without pre-existing liver disease/or patients with baseline liver parameter elevation
- Subgroup analysis of incidence of cardiovascular events (i.e. thrombo-embolic adverse events and MACE) for patients with and without cardiovascular risk factors
- Subgroup analysis of incidence of cardiovascular events (i.e. thrombo-embolic adverse events and MACE) for patients with and without pre-existing cardiovascular disease

Absolute and relative frequencies of patients with treatment emergent adverse events, count and incidence rate (including two-sided 95% CIs) of events overall and by MedDRA primary System Organ Class and Preferred Term will be calculated.

In addition, tables will be prepared to list each serious and non-serious adverse event, the number of patients who experience an event at least once, and the proportion of patients with adverse events/serious adverse events/adverse events of special interest.

Adverse events will be grouped by system organ class (SOC). Each event will be then divided into defined intensity grades (mild, moderate, and severe) by the Investigator. The tables will also divide the adverse events into those considered related to treatment (ropeginterferon alfa-2b) and those not related, as well as adverse events considered related to underlying disease PV.

The statistical analysis will be done in agreement with the ICH Topic E9, Statistical Principles for Clinical Trials and Statistical Analysis Plan (SAP) finalized and approved by the Sponsor and the study statistician before database lock. Analyses will be conducted using Statistical Analysis System (STATA®) software,

by using the last version of the dictionaries available at that timepoint.

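### The hepatobiliary ADR subgroup analyses use an outcome whose causality rule draws on the subgroup factors themselves, so they need an all-causality version beside them

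*Protocol*

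**What the plan says.** The second component of the primary endpoint in protocol section 9.7.2.1 is "treatment-emergent hepatobiliary adverse drug reactions in Part A". Section 11.1.1 defines an ADR by a suspected causal link to the product, so an adverse event the investigator judges not related does not count.

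Section 11.1.3 sets the rule for that judgement. The investigator weighs, among other things, "temporal relationship, concomitant medication, concomitant diseases and relevant history". The first sentence under *related* requires a compatible timing "and other drugs, therapeutic interventions or underlying conditions do not provide a sufficient explanation for the observed event". An event is *not related* if the timing makes causality unlikely, "or other drugs, therapeutic interventions or underlying conditions provide a sufficient explanation for the event".

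Two provisions pull the other way. The text under *related* goes on to admit cases where causality is possible "although the connection may be uncertain or doubtful". There is also a default: "Note that if causality is unknown, it should be attributed to the MP (ropeginterferon alfa-2b) until documented otherwise by the Investigator".

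The secondary objectives in section 8 ask for hepatotoxicity to be characterised in subgroups: "with/without co-medication with nonsteroidal anti-inflammatory drugs, with/without pre-existing liver disease or baseline liver parameter elevation". Section 9.7.2.5 serves this with two sets of analyses over the same factors. One uses significant elevations of liver enzymes and bilirubin. The other uses ADRs, for example the "incidence of treatment-emergent hepatobiliary adverse drug reactions for patients with and without pre-existing liver disease" or with baseline elevation. No subgroup analysis of hepatobiliary adverse events regardless of causality is listed.

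**The concern.** NSAIDs are other drugs, and pre-existing liver disease is an underlying condition. Both define the subgroups, and both are the kind of alternative explanation that section 11.1.3 allows to remove an event from the ADR count. Take two patients with the same hepatic event. The one with known liver disease has a candidate explanation on file, and the event may be judged not related. The one without has none, and the event is more likely to be counted. Outcome classification then depends on the factor under study.

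Data collection makes the alternative visible. Section 9.3.4 records pre-existing liver disease, section 9.3.5 records NSAIDs and other medication thought to affect hepatic parameters, and section 11.3.1 asks for other possible causes.

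At stake is the reading of one half of the subgroup objective. If NSAID users or patients with liver disease have more hepatobiliary events under treatment, the ADR comparison can understate that excess. Elsewhere the protocol avoids the problem: its cardiovascular endpoints and subgroups, and several of its risk-minimisation endpoints in section 9.7.2.4, use adverse events without a relatedness condition.

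**Working it through.** **What the plan gives.** The protocol states no figure for the subgroup comparison, so there is nothing to reproduce. It gives no hepatobiliary ADR rate, no subgroup shares and no expected share of events judged not related. Section 9.5 gives only an incidence for laboratory elevations (12.6% over 6 months) and 178 evaluable patients.

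**Formula.** Let R be the true ratio of all-cause treatment-emergent hepatobiliary event incidence, with versus without the factor. Let f be the share of events judged not related in patients with the factor, and g the share in patients without it. Then

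observed ADR ratio = R × (1−f)/(1−g).

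If f = g there is no bias. If f > g, the direction that section 11.1.3 favours, the observed ratio is below R. It falls below 1 when f > 1 − (1−g)/R.

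**Illustration 1 (all inputs assumed).** Incidence 15% with the factor and 10% without, so R = 1.5; g = 5%.

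- Without the factor: 10% × 0.95 = 9.5%.
- f = 20%: 15% × 0.80 = 12.0%; 12.0/9.5 = 1.26.
- f = 40%: 15% × 0.60 = 9.0%; 9.0/9.5 = 0.95.
- f = 60%: 15% × 0.40 = 6.0%; 6.0/9.5 = 0.63.
- Crossing point: 1 − 0.95/1.5 = 0.367, about 37%.

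**Range over R (assumed), with g = 0.**

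| True R | f = 10% | f = 25% | f = 50% | Below 1 when f exceeds |
|---|---|---|---|---|
| 1 | 0.90 | 0.75 | 0.50 | 0% |
| 1.5 | 1.35 | 1.125 | 0.75 | 33% |
| 2 | 1.80 | 1.50 | 1.00 | 50% |
| 3 | 2.70 | 2.25 | 1.50 | 67% |

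With g = 10% the crossing points for R = 1.5, 2 and 3 rise to 40%, 55% and 70%.

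**Illustration 2, in events.** Take 178 patients, an assumed 25% with the factor, and R = 2. Borrow 12.6% as the rate without the factor; this is an assumption, because section 9.5 gives it for laboratory elevations.

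- With the factor: 178 × 0.25 = 44.5 patients; 44.5 × 0.252 = 11.2 events.
- Without: 133.5 patients; 133.5 × 0.126 = 16.8 events.
- If half of the 11.2 are judged not related and g = 0, then 5.6 remain, 5.6/44.5 = 12.6%, and the ratio falls from 2.0 to 1.0.

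Fewer than six causality judgements would remove the whole difference in this example.

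**With the fix.** Counting all hepatobiliary adverse events sets f = g = 0, and the observed ratio equals R.

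**The case against.** The strongest case against has four parts.

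*The rule is generous to related.* An event is dropped on this ground only if the alternative explanation is sufficient; an NSAID on the medication list does not meet that by itself. Doubtful connections may still be related, and unknown causality defaults to related. This stands and keeps f down. It does not remove the problem. The default covers unknown causes, not a known and sufficient alternative. The broad wording also sits awkwardly beside the first sentence of the same category, so f may vary between investigators.

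*The objective does not rest on ADRs alone.* Section 9.7.2.5 runs the same comparisons on laboratory elevations, which are set by numeric thresholds with no relatedness judgement. This stands. A reader might infer that the whole subgroup objective gives false reassurance about hepatotoxicity. The protocol does not support that: only the ADR analyses are exposed, and a conflict with the laboratory analyses would be visible.

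*All-causality figures are already planned.* Section 9.7.2.5 tabulates all treatment-emergent adverse events by System Organ Class and Preferred Term, and splits them by relatedness. This stands for the whole cohort, so sections 9.7.2.1 and 9.7.2.2 need no change. It does not provide the figures by subgroup.

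*All-causality counts have their own bias.* Section 9.9 states that there is no control group. Patients with liver disease can have hepatobiliary events from that disease whatever the drug does, so the all-cause ratio could overstate drug risk in them. Drug-attributable incidence is a legitimate target in a safety study. This stands, and is why the all-causality analysis belongs beside the ADR analysis and should not replace it.

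That a statistical analysis plan might add the table is a weaker answer, because the protocol itself fixes ADRs as the outcome of these comparisons.

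**Conclusion.** The point holds for the hepatobiliary ADR subgroup analyses in section 9.7.2.5. The rule in section 11.1.3 lets the subgroup factors influence which events count, and the ADR ratio is biased downwards relative to the all-cause ratio whenever more events are excluded in patients with the factor than in those without. That this happens is a reasonable expectation from the wording; the protocol gives no figure for it.

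The size cannot be computed from the protocol. Modest differential exclusion attenuates a true excess. A null or reversed result needs a large share: about 37% or more of events in patients with the factor if R = 1.5 and g = 5%, both assumed. A reader might infer that the comparison necessarily shows no risk or protection; that goes beyond what the protocol supports. The laboratory-elevation component and its subgroup analyses are not affected, and the overall ADR incidence can stand as planned.

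**What to change.** In section 9.7.2.5:

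- Add the same NSAID and liver-disease or baseline-elevation subgroup analyses for all treatment-emergent hepatobiliary adverse events, regardless of causality, and show them side by side with the ADR version.
- Report, for each subgroup, the share of hepatobiliary events judged not related.
- State that absence of excess risk will not be concluded from the ADR version alone.

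The cost is wording and a few extra tables. Section 11.2 already has all adverse events recorded with the investigator's causality assessment, so no new data are needed. The downside is that the all-causality version includes events due to background liver disease, which should be said when it is interpreted.

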11.1.4 Seriousness

- A Serious Adverse Event (SAE) / Serious Adverse Drug Reaction (SADR) is any untoward medical occurrence that at any dose:
 - Results in **death**;
 - Is life-threatening;
 - Requires in-patient hospitalization or prolongation of existing hospitalization;
 - Results in a persistent or significant disability/incapacity;
 - Is a congenital anomaly/birth defect
- The term "life-threatening" refers to an event or reaction in which the patient was at risk of death at the time of the event or reaction. It does not refer to an event or reaction which hypothetically might have caused death if it were more severe.
- Medically important events:

Medical judgement should be exercised in deciding whether other situations should be considered serious. Some medical events may jeopardise the patient or may require an intervention to prevent one of the above characteristics/consequences. Such important medical events (IME) should be considered serious. The EudraVigilance Expert Working Group IME list should be consulted for assessment of medical importance.

11.1.5 Intensity

- AE intensity according to Common Terminology Criteria for Adverse Events (CTCAE) criteria, version 5.0, will be assessed as follows:
 - Grade 1 Mild; asymptomatic or mild symptoms; clinical or diagnostic observations only; intervention not indicated.

- Grade 2 Moderate; minimal, local or non-invasive intervention indicated; limiting age appropriate instrumental ADL*.
- Grade 3 Severe or medically significant but not immediately life-threatening; hospitalization or prolongation of hospitalization indicated; disabling; limiting self-care ADL**.
- Grade 4 Life-threatening consequences; urgent intervention indicated.
- Grade 5 Death related to AE.
 - *Instrumental ADL refer to preparing meals, shopping for groceries or clothes, using the telephone, managing money, etc.
 - **Self-care ADL refer to bathing, dressing and undressing, feeding self, using the toilet, taking medications, and not bedridden.
- Note: Laboratory values that are out of range i.e. CTCAE Grade 3 or higher, must be reported as AE irrespective of clinical significance assessed by the Investigator (except for the laboratory values ALT, AST, GGT and bilirubin for which an AESI documentation threshold is pre-specified [see section 9.3.1.1]).

11.1.6 Expectedness

An adverse reaction, the nature or severity of which is not consistent with the applicable product information, is considered **unexpected**. The safety profile of ropeginterferon alfa-2b is described in the current product information (Annex 1), which is defined as Reference Safety Information (RSI) for the study.

11.2 Documentation of AEs

All AEs will be collected and recorded in the eCRF over the course of the study from first ropeginterferon alfa-2b exposure to study completion (see section 9.2.2). In case of ropeginterferon alfa-2b treatment discontinuation due to hepatotoxicity, follow-up of the AE as performed in routine clinical practice (e.g. evaluation of hepatic enzymes) should be documented.

- AEs of special interest (as specified in the study protocol section 9.3.1.1), will be documented as solicited AEs.
- For each AE, the Investigator will provide the onset date and time, end date and time, treatment required, outcome, and action taken with the MP (ropeginterferon alfa-2b) and document in the eCRF AE page. It is preferred to use the medical diagnosis, or, if no diagnosis could be established at the time of AE reporting, a symptom or sign, in standard medical terminology in order to avoid the use of vague, ambiguous, or colloquial expressions.
- Each AE will be evaluated by the Investigator for:
 - seriousness
 - intensity
 - causal relationship to medicinal product exposure and
 - relationship to underlying disease PV
- The Investigator must pursue and obtain information adequate to both determine the
 outcome of the AE and to assess whether it meets the criteria for classification as a SAE
 requiring immediate notification to the Sponsor or its designated representative.
- The Investigator must ensure that the follow-up of the patient is appropriate to the nature of the event. Follow up of the patient should continue until resolution of the event or at least stabilization of the patient's clinical status and reported in the eCRF as performed in routine clinical practice.
- If the follow-up of the patient could not be conducted by the Investigator (e.g. patient was transferred to another hospital, etc.), the Investigator will do everything possible to

collect additional information by establishing and maintaining the contact with the person in charge of the patient.

